10.6.2 Listings for ECGs

All ECG measurements (ie single readings), including derivations such as change from baseline, will be listed.

All ECG measurements will be flagged with an "H" or an "L" for values that are higher or lower than their reference ranges, respectively. If applicable, data from unscheduled ECG assessments will also be listed and flagged with a "#" to indicate it will not be used in the summary statistics.

In addition, subjects with increase in QTcF interval from baseline (30-60 msec) and with 'substantial increases' (>60 msec) will be flagged with 'I' and 'SI', respectively.

A separate listing of all ECG parameters outside their reference range by subject will also be provided.

The reference ranges (from the Quotient SOP "The Interpretation of the Electrocardiogram, Vital Signs and Clinical Laboratory Data During Phase I / II Clinical Trials") and defined in Table 6 will be used.

Table 6 ECG Reference Ranges

Parameter	Split	Lower limit	Upper limit
Ventricular Rate (HR)	NA	40 bpm	100 bpm
QT Interval	NA	NA	500 msec
QTcF Interval	Male	NA	450 msec
PR Interval	NA	120 msec	220 msec
QRS Duration	NA	NA	120 msec
QRS Axis	NA	-30°	100°

HR=heart rate

NA=Not applicable

10.7 Body Weight

All body weight data will be listed. Body weight data from screening will be captured with demographic and baseline characteristics. Body weight data from admission to Part 2 will be listed separately.

10.8 Physical Examination

All physical examination details and comments on any physical examination findings will be listed by subject for all subjects. Subjects who have no clinically significant findings at post treatment time points will be reported as 'No Clinically Significant Abnormal Findings' for the purposes of the listing.

11 Interim Statistical Analyses

No interim statistical analysis is planned for this study.

12 Changes in the Conduct of the Study or Planned Analysis

12.1 Changes in the Conduct of the Study

No changes in the conduct of the study had been reported at the time this document was written.

12.2 Changes to the Planned Analyses

For consistency across study parts, the definition of Tlag in part 2 was updated to match that of Tlag in Part 1. In addition, the definition of AUCextrap has been clarified.

12.3 Any Other Relevant Changes

Not applicable.

13 Overall Considerations

13.1 Statistical Programming and Analysis

The Data Sciences Department at Quotient will perform the statistical programming and analysis to produce all analysis datasets and TFLs using the statistical SAS Software v9.4.

In general terms, categorical data will be presented using counts and percentages, whilst continuous variables will be presented using the n, mean, SD, median, minimum and maximum. For PK data, additional statistics including CV%, geometric n, geometric mean, geometric SD and geometric CV% will be presented, as appropriate. The geometric n is the

number of subjects included in the calculation of the geometric mean, geometric SD and geometric CV%.

The geometric mean is obtained by applying a natural log transformation to the raw data, calculating the arithmetic mean of the transformed values and then back transforming the arithmetic mean.

The following formula will be used to calculate the geometric SD:

$$\text{geometric SD} = \exp[\text{SD}[\log(\text{raw data})]]$$

ie a natural log transformation is applied to the raw data, the arithmetic SD of the transformed values is calculated, and then the arithmetic SD of the transformed values is back transformed.

The following formula will be used to calculate the geometric CV%:

$$\text{geometric CV\%} = 100 \times \left(\exp[\text{SD}[\log(\text{raw data})]]^2 - 1 \right)^{1/2}$$

ie a natural log transformation is applied to the raw data, the arithmetic SD of the transformed values is calculated. This value is then squared. The square value is back transformed and a value of 1 is subtracted from the back transformed value. A square root is then applied and the resulting value is multiplied by 100.

In general, summary statistics will be presented as detailed in Table 7 below, unless otherwise stated:

Table 7 Reporting Conventions for Summary Statistics

Data Type	Statistic	Number of decimal places for reporting (i)
Frequency	Counts (n)	None
	Percentages (%)	1 decimal place
	n	None
	Mean	i + 1 decimal places
	Median	i + 1 decimal places
	SD	i + 1 decimal places
	Min	i decimal places
	Max	i decimal places
	CV%	1 decimal place
	Geometric n	None
Summary statistic	Geometric Mean	i + 1 decimal places
	Geometric SD	i + 1 decimal places
	Geometric CV%	1 decimal place

i refers to the number of decimal places reported in the database or other appropriate source data for the original data

Note: The above table relates to rounding of summary stats from data received to certain number of decimal places. Summary stats on data received to a certain number of significant figures will be presented to the same number of significant figures as the data.

Details of how the PK parameters will be presented are detailed in Section 9.1.1. Where data requires rounding, values ending with 1 to 4 will be rounded down and values ending with 5 to 9 will be rounded up.

All data listings will be based on all enrolled subjects (as defined in Section 3.2.1). Details of age and sex will be included on all data listings.

If any nominal baseline measurements are found to be missing then consideration will be given to imputation using the preceding time point (eg Screening, Admission, if applicable). Unscheduled assessment may be used if appropriate. Details of any such imputations will be documented as part of the safety population.

There will be no other imputations for the safety data with regard to missing values or study discontinuation (ie subjects who do not complete the study). Imputation for PK parameter estimation using WinNonlin is described in Section 9.1.2 and for mass balance parameter estimation using SAS Software is described in Section 9.3.2. Imputations for reporting PK are described in Section 9.2.1.

If partial dates are available for smoking history, prior medications or medical/surgical history, there will be no date imputations. The data listings will only show the date information for the date part that is available (eg if only the year part of the date is available then YYYY will be presented in the listing). If the full date information is missing, then this will be presented as missing on the data listing.

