^b = these values should be listed but omitted from the descriptive statistics

NA = not applicable

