9.2.1 Bioanalytical and Pharmacokinetic Summary Tables

Summary statistics (ie n, mean, SD, coefficient of variation [CV%], median, minimum, maximum, geometric n, geometric mean, geometric SD and geometric CV%) will be presented for each study part and time point (except pre-dose time points for which geometric summary statistics will not be presented) for the following concentration data where possible:

- Part 1:

- plasma concentrations of KD025 (following Treatment A)
- plasma concentrations of [¹⁴C]-KD025 (following Treatment B)
- Part 2 (following Treatment C):
 - plasma concentrations of KD025, KD025m1 and KD025m2
 - plasma concentrations of total radioactivity
 - whole blood concentrations of total radioactivity
 - whole blood:plasma concentration ratios of total radioactivity

Imputation of non-numerical values reported in the plasma concentration data (ie values that are BLQ) will be entered as zero for the determination of summary statistics with the exception of geometric mean parameters where BLQ values will be imputed as half the LLOQ value. This also applies to any concentrations that are defined as PK parameters.

Summary statistics (ie n, mean, SD, CV%, median, minimum and maximum) will be calculated for all plasma PK parameters by study part and analyte as follows. Geometric n, geometric mean, geometric SD and geometric CV% will be presented for all PK parameters except Tlag and Tmax.

- Part 1:
 - plasma PK parameters of KD025 (following Treatment A)
 - plasma PK parameters of [¹⁴C]-KD025 (following Treatment B)
- Part 2 (following Treatment C):
 - plasma PK parameters of KD025, KD025m1 and KD025m2 and total radioactivity
- Part 1/Part 2:
 - Relative Bioavailability of tablet to capsule formulation

Data recorded as not reportable/no result (NR) or no sample (NS) will be handled as missing, ie no assumption will be made about the actual concentration. If applicable, parameters recorded as not calculated (NC) will be handled as missing.

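### The geometric CV% formula displayed in SAP 13.1 puts the square outside the exponential and contradicts the correct description directly below it

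*SAP*

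**What the plan says.** SAP 13.1 introduces two displayed formulas as the ones to be applied. The geometric SD is given as "geometric SD} = \exp[\text{SD}[\log(\text{raw data" with the brackets closed, that is, exp(s), where s is the SD of the natural-log data. The geometric CV% is 100 times the square root of "\exp[\text{SD}[\log(\text{raw data})]]^2 - 1".

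A sentence beneath the second formula restates it in words. After the log transformation, "the arithmetic SD of the transformed values is calculated. This value is then squared". Then: "The square value is back transformed and a value of 1 is subtracted from the back transformed value". A square root and multiplication by 100 follow.

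SAP 9.2.1 sets where the statistic appears: "Geometric n, geometric mean, geometric SD and geometric CV% will be presented for all PK parameters except Tlag and Tmax". It also applies to the concentration summaries, except at pre-dose time points. The lambda-z limits are excluded by a footnote to SAP Table 2: "these values should be listed but omitted from the descriptive statistics". F based on Cmax and on AUC(0-inf) are parameters in that table, and F is a primary endpoint (SAP 4.3.1). Protocol 15.4 lists geometric CV% but gives no formula.

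**The concern.** The display and the sentence explaining it are different calculations. In the display both square brackets close before the exponent, so what is squared is exp(s), the geometric SD defined just above. In the sentence, what is squared is s. Only the second is the CV of a log-normal variable.

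A programmer who stores the geometric SD and then follows the display would square that stored value and obtain the wrong answer. The study is small (6 subjects, to secure 4 evaluable) and purely descriptive, so a reader judges the variability of F from the spread statistics in the tables. An inflated geometric CV% would make absolute bioavailability look far more variable than it is.

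**Working it through.** The documents state no CV and no sample size calculation, so there is no plan figure to reproduce. The check compares the two rules.

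**Inputs.** The displayed formula and its verbal description come from SAP 13.1. The log-scale SD s is not given anywhere and is varied as an assumption.

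**Formulas.**
- Display, read literally: L(s) = 100 × sqrt((exp(s))² − 1) = 100 × sqrt(exp(2s) − 1).
- Description: T(s) = 100 × sqrt(exp(s²) − 1).

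**Where they agree.** L = T requires 2s = s², so s = 0 or s = 2. Between these values L is larger; above s = 2 it is smaller.

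**Size.** For a true geometric CV of c (as a fraction), s = sqrt(ln(1 + c²)). For c = 0.30, s = sqrt(ln 1.09) = 0.2936, and L = 100 × sqrt(exp(0.5872) − 1) = 89.4%.

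| True geometric CV (description) | s | Value from display | Ratio |
|---|---|---|---|
| 5% | 0.050 | 32.4% | 6.48 |
| 10% | 0.100 | 47.0% | 4.70 |
| 20% | 0.198 | 69.7% | 3.49 |
| 30% | 0.294 | 89.4% | 2.98 |
| 50% | 0.472 | 125.4% | 2.51 |
| 80% | 0.703 | 175.6% | 2.19 |
| 100% | 0.833 | 207.0% | 2.07 |
| 150% | 1.086 | 278.7% | 1.86 |
| 200% | 1.269 | 341.2% | 1.71 |

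Solving for the crossing points, the ratio is 5 at a true CV of 8.7% (s = 0.087), 2 at 114% (s = 0.914) and 1 at 732% (s = 2). The error is proportionally largest where the data are tightest.

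**Illustration with six assumed F values** (40, 48, 55, 62, 70, 85%; not trial data):
- Log SD s = 0.2693, so the geometric SD is exp(0.2693) = 1.309.
- Description: 100 × sqrt(exp(0.0725) − 1) = 27.4%.
- Display: 100 × sqrt(1.309² − 1) = 84.5%.
- Arithmetic CV for comparison: the mean is 60, the squared deviations sum to 1298, the SD is sqrt(1298/5) = 16.11, and the CV is 26.9%.

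**Reach.** Affected: the geometric CV% of F, of the other summarised PK parameters and of the post-dose concentration summaries. Not affected: Tlag and Tmax ("geometric CV% will be presented for all PK parameters except Tlag and Tmax"), the lambda-z limits, and the mass balance tables, for which SAP 9.4.1 plans no geometric statistics.

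**The case against.** The strongest reply is that the plan already contains the right rule. The sentence below the display is offered as its explanation, goes step by step and is unambiguous. A programmer who follows it gets the correct value. This stands: the defect may be only a slip of notation.

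Second, the text was read from PDF by a program, and the whole point turns on the position of one exponent. A misread superscript cannot be excluded. This also stands, and it is why the original page must be checked first.

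Third, an error would probably be noticed. SAP 13.2 provides for peer review of SAS code, and 13.2.1 for recalculation by calculator or spreadsheet. Mock Table 14.2.2.1 prints CV%, geometric SD and geometric CV% in one column, so in the illustration 84.5% would stand beside 26.9%. Individual parameters are listed, so anyone could recompute the figure. This lowers the risk but does not remove it, because neither QC section says which of the two rules is the reference. A reader might go further and infer that QC would confirm the wrong value. The documents do not support that, since they do not say that QC works from the display.

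Fourth, geometric CV% is not the only measure of spread. SD, CV%, minimum, maximum and geometric SD are also planned. No formal PK analysis is planned (SAP 9.2.4), so no test depends on it.

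**Conclusion.** In the text as supplied, SAP 13.1 gives two incompatible rules for one reported statistic. The displayed rule is wrong and the worded rule is right. If the display is followed, the geometric CV% of the affected quantities is overstated about 2- to 5-fold, provided the true geometric CV is about 9% to 114%. Below that range the inflation exceeds 5-fold. Above it the inflation falls under 2-fold, and it reverses beyond s = 2. The range is an assumption about variability, not a figure from the documents.

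A reader might infer that the spread of every PK parameter will be misreported, or that the bioavailability result itself is wrong. Neither follows. Some parameters receive no geometric CV%. The harm arises only if the display is used in place of the description. Geometric means, geometric SDs and the point estimates of F do not use this formula. What remains is a real but conditional inconsistency that is worth correcting because it touches the spread reported for a primary endpoint.

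**What to change.** Check the exponent against the original SAP page. If it reads as supplied, change the display in SAP 13.1 to: geometric CV% = 100 × (exp[(SD[log(raw data)])²] − 1)^(1/2). The square then sits on the log-scale SD and the display matches the description. Add one sentence naming this as the formula for both SAS programming and the manual QC in SAP 13.2.1.

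The cost is a one-line correction, with no change to data, design or any other planned output. If the original page already shows the square inside the exponential, no change to the formula is needed.

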13.2 Quality Control of Summary Tables, Figures and Listings

Isolated data errors detected as a result of the QC checks that are deemed significant (ie errors that would impact the interpretation of the results in relation to the study objectives) will be corrected as per the data management plan. Systematic data errors will be investigated further. The data will be corrected if necessary, and the appropriate table, figure, and/or listing re-generated and then re-checked.

In addition to QC checks, a documented peer review will be performed of all SAS Software-generated report standard summary tables, figures and data listings, including a review of SAS Software code and program log files.

13.2.1 Quality Control - Summary Tables

Manual QC methods (ie comparison of results in the table to results calculated by a calculator or spreadsheet) will be used for all summary tables. All summary tables will be QC'd as follows:

- for tables presented by study part only (ie no time points), all summary statistics will be QC'd
- for tables presented by study part and time point, at least one time point in each table will be QC'd – different combinations of time point will be selected across tables
- where tables are produced using a macro for multiple parameters, a minimum of 3 tables, using study part and time point as appropriate, will be QC'd
- for AEs, the study part/treatment details will be 100% QC'd against the treatment allocation list for all subjects
- AE summary tables will be 100% checked using the relevant data listing

13.2.2 Quality Control - Figures

All figures will be QC'd manually using the corresponding/appropriate summary table or data listing, as follows:

- all data points for treatment will be checked
- where figures are produced using a macro for individual subjects and/or multiple parameters, a minimum of 3 figures will be QC'd
- mean figures will be QC'd using the corresponding summary table

13.2.3 Quality Control - Data Listings

All data listings will be subjected to a 100% manual QC check against the study database or other appropriate source data for a minimum of 2 subjects. If appropriate, the subjects checked will include at least one subject who withdrew early from the study.

14 SAS Data Transfer

All SAS datasets used for analysis and reporting will be transferred to Kadmon on issue of the final CSR. This will be performed in compliance with CDISC ADaM (IG v1.1), data will be transferred as SAS Software transport files and will include define.xml (v2.0) output as well as a Data Reviewers Guide in pdf, which will be linked to the ADaM define.xml.

In addition, KD025m1 and KD025m2 Part 1 data provided by Covance will not be reported or analysed but will be transferred to Kadmon as raw data and will be included in the SDTM datasets

15 Programming Conventions

Quotient standards for layout of tables, figures and data listings and programming conventions will be used as follows:

- courier new, font size 8
- landscape
- US letter size (8.5 x 11 inches)

Tables and listings will be produced as MS Word 2016 documents and figures will be produced as PDF files. Listings will be sorted by subject ID number and treatment (where applicable).

The mock tables (Section 20) presented are a representation of Quotient reporting standards. However these are provided for illustrative purposes only. The numbering and titles of all TFLs and the formatting, labelling, footnotes and cosmetic appearance of tables may be modified or additional labelling/footnotes may need to be added during analysis and reporting, for clarification purposes. Any such changes will not be regarded as changes to planned analyses.

16 Reference List

[1] International Council for Harmonisation (ICH) Topic E 14, The Clinical Evaluation of QT/QTc Interval Prolongation and Proarrhythmic Potential for Non-Antiarrhythmic Drugs Guidelines approved by the Committee for Medicinal Products for Human Use (CHMP) in May 2005 which came into force November 2005.

17 Index of Tables

Table Number	Table Title
	Subject Disposition, Populations and Datasets
14.1.1	Subject Disposition by Reason Summary Statistics: All Enrolled Subjects Part 1 & Part 2
14.1.2.1	Analysis Populations Summary Statistics: All Enrolled Subjects Part 1 & Part 2
14.1.2.2	Analysis Datasets Summary Statistics: PK Population Part 1 & Part 2 (Programming note: Only produce table if there is a PK analysis dataset. If no PK or mass balance analysis dataset defined then do not produce table 14.1.2.2 or 14.1.2.3, and re-number table 14.1.2.1 as 14.1.2)
14.1.2.3	Analysis Datasets Summary Statistics: Mass Balance Population Part 1 & Part 2 (Programming note: Only produce table if there is a mass balance analysis dataset defined. If no PK or mass balance dataset defined then do not produce table 14.1.2.2 or 14.1.2.3, and re-number table 14.1.2.1 as 14.1.2. If there is a mass balance dataset but no PK dataset, then do not produce table 14.1.2.2 and re-number table 14.1.2.3 as 14.1.2.2)
	Demographic and Baseline Characteristics
14.1.3	Demographic and Baseline Characteristics Summary Statistics: Safety Population Part 1 & Part 2
14.1.4	Lifestyle Details: Smoking History and Alcohol Consumption at Baseline Summary Statistics: Safety Population Part 1 & Part 2
	Dosing Details
14.1.5.1	Extent of Exposure Summary Statistics: Safety Population Part 1
14.1.5.2	Extent of Exposure Summary Statistics: Safety Population Part 2
	Plasma and Whole Blood Pharmacokinetic Concentrations

Table Number	Table Title
14.2.1.1	Plasma Pharmacokinetic Concentrations Summary Statistics: <PK Population/PK Analysis Dataset> Part 1: KD025 Oral Tablet & [14C]-KD025 IV Infusion <KD025 / [14C]-KD025 (units)>
14.2.1.2.1	Plasma Pharmacokinetic Concentrations Summary Statistics: <PK Population/PK Analysis Dataset> Part 2: [14C]-KD025 Oral Capsule <KD025 / KD025m1 / KD025m2 (units)>
14.2.1.2.2	Plasma Pharmacokinetic Concentrations: Total Radioactivity Summary Statistics: <PK Population/PK Analysis Dataset> Part 2: [14C]-KD025 Oral Capsule
14.2.1.2.3	Whole Blood Pharmacokinetic Concentrations: Total Radioactivity Summary Statistics: <PK Population/PK Analysis Dataset> Part 2: [14C]-KD025 Oral Capsule
14.2.1.2.4	Whole Blood:Plasma Concentration Ratios: Total Radioactivity Summary Statistics: <PK Population/PK Analysis Dataset> Part 2: [14C]-KD025 Oral Capsule
Plasma and Whole Blood Pharmacokinetic Parameters	
14.2.2.1	Plasma Pharmacokinetic Parameters Summary Statistics: <PK Population/PK Analysis Dataset> Part 1: KD025 Oral Tablet & [14C]-KD025 IV Infusion < KD025 / [14C]-KD025 >
14.2.2.2.1	Plasma Pharmacokinetic Parameters Summary Statistics: <PK Population/PK Analysis Dataset> Part 2: [14C]-KD025 Oral Capsule < KD025 / KD025m1 / KD025m2 >
14.2.2.2.2	Plasma Pharmacokinetic Parameters: Total Radioactivity Summary Statistics: <PK Population/PK Analysis Dataset> Part 2: [14C]-KD025 Oral Capsule
14.2.2.2.3	Whole Blood Pharmacokinetic Parameters: Total Radioactivity Summary Statistics: <PK Population/PK Analysis Dataset> Part 2: [14C]-KD025 Oral Capsule
14.2.2.3	Relative Bioavailability of Oral Formulations: KD025 Summary Statistics: <PK Population/PK Analysis Dataset> Part 1 & Part 2
Excretion and Recovery – Urine Concentrations	
14.2.3.1.1	Excretion: Total Radioactivity Ae(Urine) by Collection Period <Units> Summary Statistics: <Mass Balance Population/Mass Balance Analysis Dataset> Part 2: [14C]-KD025 Oral Capsule

Table Number	Table Title
14.2.3.1.2	Excretion: Total Radioactivity Cumulative Ae(Urine) <Units> Summary Statistics: <Mass Balance Population/Mass Balance Analysis Dataset> Part 2: [14C]-KD025 Oral Capsule
14.2.3.1.3	Recovery: Total Radioactivity %Ae(Urine) by Collection Period Summary Statistics: <Mass Balance Population/Mass Balance Analysis Dataset> Part 2: [14C]-KD025 Oral Capsule
14.2.3.1.4	Recovery: Total Radioactivity Cumulative %Ae(Urine) Summary Statistics: <Mass Balance Population/Mass Balance Analysis Dataset> Part 2: [14C]-KD025 Oral Capsule
	Excretion and Recovery – Faecal Concentrations
14.2.3.2.1	Excretion: Total Radioactivity Ae(Faeces) by Collection Period <Units> Summary Statistics: <Mass Balance Population/Mass Balance Analysis Dataset> Part 2: [14C]-KD025 Oral Capsule
14.2.3.2.2	Excretion: Total Radioactivity Cumulative Ae(Faeces) <Units> Summary Statistics: <Mass Balance Population/Mass Balance Analysis Dataset> Part 2: [14C]-KD025 Oral Capsule
14.2.3.2.3	Recovery: Total Radioactivity %Ae(Faeces) by Collection Period Summary Statistics: <Mass Balance Population/Mass Balance Analysis Dataset> Part 2: [14C]-KD025 Oral Capsule
14.2.3.2.4	Recovery: Total Radioactivity Cumulative %Ae(Faeces) Summary Statistics: <Mass Balance Population/Mass Balance Analysis Dataset> Part 2: [14C]-KD025 Oral Capsule
	Excretion and Recovery – Urine and Faeces Combined
14.2.3.3.1	Excretion: Total Radioactivity Ae(Total) by Collection Period <Units> Summary Statistics: <Mass Balance Population/Mass Balance Analysis Dataset> Part 2: [14C]-KD025 Oral Capsule

Table Number	Table Title
14.2.3.3.2	Excretion: Total Radioactivity Cumulative Ae(Total) <Units> Summary Statistics: <Mass Balance Population/Mass Balance Analysis Dataset> Part 2: [14C]-KD025 Oral Capsule
14.2.3.3.3	Recovery: Total Radioactivity %Ae(Total) by Collection Period Summary Statistics: <Mass Balance Population/Mass Balance Analysis Dataset> Part 2: [14C]-KD025 Oral Capsule
14.2.3.3.4	Recovery: Total Radioactivity Cumulative %Ae(Total) Summary Statistics: <Mass Balance Population/Mass Balance Analysis Dataset> Part 2: [14C]-KD025 Oral Capsule
	Cumulative Excretion and Recovery Parameters
14.2.3.4	Excretion and Recovery: Total Radioactivity Overall Cumulative Excretion and Recovery Parameters Summary Statistics: <Mass Balance Population/Mass Balance Analysis Dataset> Part 2: [14C]-KD025 Oral Capsule
	Adverse Events
14.3.1.1	Overall Summary of Treatment-Emergent Adverse Events Summary Statistics: Safety Population Part 1: KD025 Oral Tablet & [14C]-KD025 IV Infusion
14.3.1.2	Subjects Reporting Treatment-Emergent Adverse Events By MedDRA System Organ Class and Preferred Term Summary Statistics: Safety Population Part 1: KD025 Oral Tablet & [14C]-KD025 IV Infusion
14.3.1.3	Subjects Reporting Treatment-Emergent Adverse Events By MedDRA System Organ Class, Preferred Term and Severity Summary Statistics: Safety Population Part 1: KD025 Oral Tablet & [14C]-KD025 IV Infusion
14.3.1.4	Subjects Reporting Treatment-Emergent Adverse Events By MedDRA System Organ Class, Preferred Term and Relationship to IMP Summary Statistics: Safety Population Part 1: KD025 Oral Tablet & [14C]-KD025 IV Infusion
14.3.1.5	Subjects Reporting Adverse Drug Reactions By MedDRA System Organ Class and Preferred Term Summary Statistics: Safety Population Part 1: KD025 Oral Tablet & [14C]-KD025 IV Infusion

Table Number	Table Title
14.3.1.6	Subjects Reporting Serious Adverse Events By MedDRA System Organ Class and Preferred Term Summary Statistics: Safety Population Part 1: KD025 Oral Tablet & [14C]-KD025 IV Infusion
14.3.2.1	Overall Summary of Treatment-Emergent Adverse Events Summary Statistics: Safety Population Part 2: [14C]-KD025 Oral Capsule
14.3.2.2	Subjects Reporting Treatment-Emergent Adverse Events By MedDRA System Organ Class and Preferred Term Summary Statistics: Safety Population Part 2: [14C]-KD025 Oral Capsule
14.3.2.3	Subjects Reporting Treatment-Emergent Adverse Events By MedDRA System Organ Class, Preferred Term and Severity Summary Statistics: Safety Population Part 2: [14C]-KD025 Oral Capsule
14.3.2.4	Subjects Reporting Treatment-Emergent Adverse Events By MedDRA System Organ Class, Preferred Term and Relationship to IMP Summary Statistics: Safety Population Part 2: [14C]-KD025 Oral Capsule
14.3.2.5	Subjects Reporting Adverse Drug Reactions By MedDRA System Organ Class and Preferred Term Summary Statistics: Safety Population Part 2: [14C]-KD025 Oral Capsule
14.3.2.6	Subjects Reporting Serious Adverse Events By MedDRA System Organ Class and Preferred Term Summary Statistics: Safety Population Part 2: [14C]-KD025 Oral Capsule
	Laboratory Results
14.4.1.1	Haematology Summary Statistics: Safety Population Part 1: KD025 Oral Tablet & [14C]-KD025 IV Infusion
14.4.1.2	Haematology Shift Table: Safety Population Part 1: KD025 Oral Tablet & [14C]-KD025 IV Infusion
14.4.1.3	Clinical Chemistry Summary Statistics: Safety Population Part 1: KD025 Oral Tablet & [14C]-KD025 IV Infusion
14.4.1.4	Clinical Chemistry Shift Table: Safety Population Part 1: KD025 Oral Tablet & [14C]-KD025 IV Infusion

Table Number	Table Title
14.4.2.1	Haematology Summary Statistics: Safety Population Part 2: [14C]-KD025 Oral Capsule
14.4.2.2	Haematology Shift Table: Safety Population Part 2: [14C]-KD025 Oral Capsule
14.4.2.3	Clinical Chemistry Summary Statistics: Safety Population Part 2: [14C]-KD025 Oral Capsule
14.4.2.4	Clinical Chemistry Shift Table: Safety Population Part 2: [14C]-KD025 Oral Capsule
	Vital Signs and ECG Results
14.5.1.1	Vital Signs Summary Statistics: Safety Population Part 1: KD025 Oral Tablet & [14C]-KD025 IV Infusion
14.5.1.2.1	ECGs Summary Statistics: Safety Population Part 1: KD025 Oral Tablet & [14C]-KD025 IV Infusion
14.5.1.2.2	ECGs QTcF Categorical Data Summary Statistics: Safety Population Part 1: KD025 Oral Tablet & [14C]-KD025 IV Infusion
14.5.2.1	Vital Signs Summary Statistics: Safety Population Part 2: [14C]-KD025 Oral Capsule
14.5.2.2.1	ECGs Summary Statistics: Safety Population Part 2: [14C]-KD025 Oral Capsule
14.5.2.2.2	ECGs QTcF Categorical Data Summary Statistics: Safety Population Part 2: [14C]-KD025 Oral Capsule

18 Index of Figures

Figure Number	Figure Title
	Whole Blood and Plasma Pharmacokinetic Concentrations
14.2.2.1.1	Plasma Pharmacokinetic Concentrations Linear/Linear Scale Arithmetic Mean (\pm Arithmetic SD) Values: <PK Population/PK Analysis Dataset> Part 1: KD025 Oral Tablet & [14C]-KD025 IV Infusion < KD025 / [14C]-KD025 >
14.2.2.1.2	Plasma Pharmacokinetic Concentrations Log10/Linear Scale Geometric Mean (\times/\div Geometric SD) Values: <PK Population/PK Analysis Dataset> Part 1: KD025 Oral Tablet & [14C]-KD025 IV Infusion < KD025 / [14C]-KD025 >
14.2.2.1.3	Plasma Pharmacokinetic Concentrations Linear/Linear Scale Spaghetti Plots of All Individual Values: <PK Population/PK Analysis Dataset> Part 1: KD025 Oral Tablet & [14C]-KD025 IV Infusion < KD025 / [14C]-KD025 >
14.2.2.1.4	Plasma Pharmacokinetic Concentrations Log10/Linear Scale Spaghetti Plots of All Individual Values: <PK Population/PK Analysis Dataset> Part 1: KD025 Oral Tablet & [14C]-KD025 IV Infusion < KD025 / [14C]-KD025 >
14.2.2.2.1	Plasma Pharmacokinetic Concentrations Linear/Linear Scale Arithmetic Mean (\pm Arithmetic SD) Values: <PK Population/PK Analysis Dataset> Part 2: [14C]-KD025 Oral Capsule (Programming note: KD025, KD025m1, KD025m2 and total radioactivity will be overlaid on the same plot)
14.2.2.2.2	Plasma Pharmacokinetic Concentrations Log10/Linear Scale Geometric Mean (\times/\div Geometric SD) Values: <PK Population/PK Analysis Dataset> Part 2: [14C]-KD025 Oral Capsule (Programming note: KD025, KD025m1, KD025m2 and total radioactivity will be overlaid on the same plot)

Figure Number	Figure Title
14.2.2.2.3	
Plasma and Whole Blood Pharmacokinetic Concentrations: Total Radioactivity
 
Linear/Linear Scale
 
Arithmetic Mean (\pm Arithmetic SD) Values: <PK Population/PK Analysis Dataset>
 
Part 2: [14C]-KD025 Oral Capsule
 
(Programming note: Plasma and whole blood total radioactivity concentrations will be overlaid on the same plot)

14.2.2.2.4	
Plasma and Whole Blood Pharmacokinetic Concentrations: Total Radioactivity
 
Log10/Linear Scale
 
Geometric Mean (\times/\div Geometric SD) Values: <PK Population/PK Analysis Dataset>
 
Part 2: [14C]-KD025 Oral Capsule
 
(Programming note: Plasma and whole blood total radioactivity concentrations will be overlaid on the same plot)

14.2.2.2.5	
Plasma Pharmacokinetic Concentrations
 
Linear/Linear Scale
 
Spaghetti Plots of All Individual Values: <PK Population/PK Analysis Dataset>
 
Part 2: [14C]-KD025 Oral Capsule
 
<Analyte>
 
(Programming note: KD025, KD025m1 and KD025m2 will be displayed on separate pages)

14.2.2.2.6	
Plasma Pharmacokinetic Concentrations
 
Log10/Linear Scale
 
Spaghetti Plots of All Individual Values: <PK Population/PK Analysis Dataset>
 
Part 2: [14C]-KD025 Oral Capsule
 
<Analyte>
 
(Programming note: KD025, KD025m1 and KD025m2 will be displayed on separate pages)

Figure Number	Figure Title
14.2.2.2.7	
Plasma and Whole Blood Pharmacokinetic Concentrations: Total Radioactivity
 
Linear/Linear Scale
 
Spaghetti Plots of All Individual Values: <PK Population/PK Analysis Dataset>
 
Part 2: [14C]-KD025 Oral Capsule
 
<Plasma/Whole Blood Total Radioactivity>
 
(Programming note: Plasma and whole blood total radioactivity will be displayed on separate pages)

14.2.2.2.8	
Plasma and Whole Blood Pharmacokinetic Concentrations: Total Radioactivity
 
Log10/Linear Scale
 
Spaghetti Plots of All Individual Values: <PK Population/PK Analysis Dataset>
 
Part 2: [14C]-KD025 Oral Capsule
 
<Plasma/Whole Blood Total Radioactivity>
 
(Programming note: Plasma and whole blood total radioactivity will be displayed on separate pages)

14.2.2.2.9	
Plasma and Whole Blood Pharmacokinetic Concentrations
 
Linear/Linear Scale
 
Individual Values for Subject <xxx>: <PK Population/PK Analysis Dataset>
 
Part 2: [14C]-KD025 Oral Capsule
 
<Subject>
 
(Programming note: KD025, KD025m1, KD025m2 and total radioactivity [plasma and whole blood] will be overlaid on the same plot)

14.2.2.2.10	
Plasma and Whole Blood Pharmacokinetic Concentrations
 
Log10/Linear Scale
 
Individual Values for Subject <xxx>: <PK Population/PK Analysis Dataset>
 
Part 2: [14C]-KD025 Oral Capsule
 
<Subject>
 
(Programming note: KD025, KD025m1, KD025m2 and total radioactivity [plasma and whole blood] will be overlaid on the same plot)

Figure Number	Figure Title
14.2.2.3.1	Plasma Pharmacokinetic Concentrations: Oral Formulations, KD025 Linear/Linear Scale Arithmetic Mean (\pm Arithmetic SD) Values: <PK Population/PK Analysis Dataset> Part 1 and 2 (Programming note: Treatments A and C will be overlaid on the same plot)
14.2.2.3.2	Plasma Pharmacokinetic Concentrations: Oral Formulations, KD025 Log10/Linear Scale Geometric Mean (\times/\div Geometric SD) Values: <PK Population/PK Analysis Dataset> Parts 1 and 2 (Programming note: Treatments A and C will be overlaid on the same plot)
	Cumulative Excretion and Recovery
14.2.3.1	Mean Cumulative Excretion of Total Radioactivity CumAe(Urine), CumAe(Faeces) and CumAe(Total) Linear/Linear Scale Arithmetic Mean (\pm Arithmetic SD) Values: <Mass Balance Population/Mass Balance Analysis Dataset> Part 2: [14C]-KD025 Oral Capsule
14.2.3.2	Mean Cumulative Recovery of Total Radioactivity Cum%Ae(Urine), Cum%Ae(Faeces) and Cum%Ae(Total) Linear/Linear Scale Arithmetic Mean (\pm Arithmetic SD) Values: <Mass Balance Population/Mass Balance Analysis Dataset> Part 2: [14C]-KD025 Oral Capsule

19 Index of Listings

Listing Number	Listing Title	
Subject Informed Consent and Completion/Withdrawal		
16.2.1	Subject Informed Consent and Completion/Withdrawal Individual Values: All Enrolled Subjects Part 1 & Part 2	
Protocol Deviations and Inclusion/Exclusion Criteria		
16.2.2.1	Protocol Deviations Individual Values: All Enrolled Subjects Part 1 & Part 2	
16.2.2.2	Inclusion/Exclusion Criteria Individual Values: All Enrolled Subjects Part 1 & Part 2	
Analysis Populations and Reasons for Exclusion		
16.2.3.1	Analysis Populations and Reasons for Exclusion Individual Values: All Enrolled Subjects Part 1 & Part 2 (Programming note: If analysis datasets are not required, then this listing will be re-numbered from 16.2.3.1 to 16.2.3 and Listing 16.2.3.2 will not be produced)	
16.2.3.2	Analysis Datasets and Reasons for Exclusion Individual Values: All Enrolled Subjects Part 1 & Part 2 (Programming note: If analysis datasets are not required, then this listing will not be produced and Listing 16.2.3.1 will be re-numbered from 16.2.3.1 to 16.2.3)	
Demographic and Baseline Characteristics		
16.2.4.1	Demographics and Baseline Characteristics Individual Values: All Enrolled Subjects Part 1 & Part 2	
16.2.4.2	Lifestyle Details: Smoking History and Alcohol Consumption Individual Values: All Enrolled Subjects Part 1 & Part 2	
16.2.4.3	Medical/Surgical History Individual Values: All Enrolled Subjects Part 1 & Part 2	
16.2.4.4	Prior and Concomitant Medication Individual Values: All Enrolled Subjects Part 1 & Part 2	

Listing Number	Listing Title
16.2.4.5	Urine Drug Screen Individual Values: All Enrolled Subjects Part 1 & Part 2
16.2.4.6	Alcohol Breath and Carbon Monoxide Breath Test Individual Values: All Enrolled Subjects Part 1 & Part 2
16.2.4.7	Virology Individual Values: All Enrolled Subjects Part 1 & Part 2
16.2.4.8	Creatinine Clearance Individual Values: All Enrolled Subjects Part 1 & Part 2
	Dosing Details and Meal Details
16.2.5.1.1	Dosing Details Individual Values: All Enrolled Subjects Part 1 & Part 2
16.2.5.1.2	Meal Details Individual Values: All Enrolled Subjects Part 1 & Part 2
	Urine and Faecal Concentration Data
16.2.5.2.1	Urine Collection and Weight Details Individual Values: All Enrolled Subjects Part 2: [14C]-KD025 Oral Capsule
16.2.5.2.2	Urine Concentrations, Excretion and Recovery: Total Radioactivity (units) Individual Values: All Enrolled Subjects Part 2: [14C]-KD025 Oral Capsule
16.2.5.2.3	Faecal Collection and Weight Details Individual Values: All Enrolled Subjects Part 2: [14C]-KD025 Oral Capsule
16.2.5.2.4	Faecal Concentrations, Excretion and Recovery: Total Radioactivity (units) Individual Values: All Enrolled Subjects Part 2: [14C]-KD025 Oral Capsule
16.2.5.2.5	Total Urine and Faecal Concentrations, Excretion and Recovery: Total Radioactivity (units) Individual Values: All Enrolled Subjects Part 2: [14C]-KD025 Oral Capsule
	Plasma and Whole Blood Pharmacokinetic Concentration Data

Listing Number	Listing Title
16.2.5.3.1.1	Blood Sample Collection Details for Pharmacokinetic Analysis Individual Values: All Enrolled Subjects Part 1: KD025 Oral Tablet & [14C]-KD025 IV Infusion
16.2.5.3.1.2	Plasma Pharmacokinetic Concentrations Individual Values: All Enrolled Subjects Part 1: KD025 Oral Tablet & [14C]-KD025 IV Infusion < KD025 / [14C]-KD025 >
16.2.5.3.2.1	Blood Sample Collection Details for Pharmacokinetic Analysis Individual Values: All Enrolled Subjects Part 2: [14C]-KD025 Oral Capsule
16.2.5.3.2.2	Plasma Pharmacokinetic Concentrations Individual Values: All Enrolled Subjects Part 2: [14C]-KD025 Oral Capsule < KD025 / KD025m1 / KD025m2 >
16.2.5.3.2.3	Plasma and Whole Blood Pharmacokinetic Concentrations: Total Radioactivity Individual Values: All Enrolled Subjects Part 2: [14C]-KD025 Oral Capsule (Programming note: This listing will include whole blood:plasma concentration ratios)
	Plasma and Whole Blood Pharmacokinetic Parameter Data
16.2.6.1.1	Plasma Pharmacokinetic Parameters Individual Values: All Enrolled Subjects Part 1: KD025 Oral Tablet & [14C]-KD025 IV Infusion < KD025 / [14C]-KD025 >
16.2.6.2.1	Plasma Pharmacokinetic Parameters Individual Values: All Enrolled Subjects Part 2: [14C]-KD025 Oral Capsule < KD025 / KD025m1 / KD025m2 >
16.2.6.2.2	Plasma and Whole Blood Pharmacokinetic Parameters: Total Radioactivity Individual Values: All Enrolled Subjects Part 2: [14C]-KD025 Oral Capsule <Plasma/Whole Blood>
